#### *7.1.1.3 Treatment arm 3: Standard support plus medication management with contingency management (SS+MM+CM)*

Although available evidence suggests that MM enhances adherence to prescribed medication for relapse prevention in alcohol dependence, there is concern that attendance at MM sessions may be sub-optimal (77). To optimise attendance, participants will follow the same care pathway as those in the SS+MM arm of the trial but with the addition of CM. Incentives in the form of vouchers (not redeemable for alcohol) will be provided to reinforce attendance at MM sessions by telephone with the pharmacist. The CM procedure and value of the incentives has been informed by the available literature on CM in substance misusers (69) and alcohol dependence (13) and focus groups with service users with experience with treatment services for alcohol dependence. Participants will receive between £2 and £10 in the form of a voucher for each MM session completed, with a total value of up to £120 for completing all support sessions. After each MM session a SMS text message will be sent to the participant to inform them that they have been awarded a voucher, the magnitude of the voucher and the total voucher value received to date.

#### *7.1.1.4 Intervention training*

All pharmacists delivering the MM and CM interventions will receive adequate training, specifically designed for the study, prior to commencement of delivery of the interventions and will cover all aspects of the research protocol and the medication management and contingency management protocols.

### 7.1.2 Target population

The population will be currently abstinent alcohol dependent adults within the first month of prescription of acamprosate and who are both willing and able to provide informed consent to take part in the research.

### 7.1.3 Inclusion/exclusion criteria

Inclusion and exclusion criteria have been selected so that the sample population will be broadly representative of the target population as a whole. The decision to prescribe acamprosate will be made by the service users treating clinician in the conjunction with the service user, the research team will not be part of this decision.

#### *7.1.3.1 Inclusion criteria*

- Adult aged  $\geq$  18 years
- An ICD-10 diagnosis alcohol dependence,
- Currently abstinent from alcohol,
- Prescribed acamprosate by treating clinician
- Willing to provide informed consent to take part in the trial.

#### *7.1.3.2 Exclusion criteria*

- Severe physical/mental illness likely to preclude active participation in treatment or follow up,
- Current participation in another trial
- Unable to adequately understand verbal English
- Current dependence on an illicit substance

#### 7.1.4 Setting/context

Participants for the current research will be recruited from specialist alcohol treatment services based in England. SS will be provided by these specialist services and the participants' General Practitioner as per current standard practice. MM and CM will be administered by pharmacists via a central telephone support service in the UK.

#### 7.1.5 Sampling

Recruitment will take place for 3 months for the pilot phase of the trial, to assess recruitment rates.

#### 7.1.6 Study entry

Following referral to the specialist alcohol service all service users who meet the inclusion criteria will be identified by the specialist alcohol service.

##### *7.1.6.1 Informed consent*

Potential participants will be initially contacted by a member of their specialist alcohol service to ask if they would be willing to speak with a member of the research team about the research trial. In addition, a poster advertising that the research is taking place will be placed in the participating specialist alcohol services to give service users the opportunity to express an interest in taking part with their key worker. A member of the research team will subsequently contact the service user to provide details of the nature and purpose of the research. If the service user expresses that they wish to continue with the research process a participant information sheet will be given. An information sheet will be given to the potential participant. An initial assessment appointment will be made at least 24 hours after the study information sheet has been given to allow time to consider the information and ask any questions. Informed consent to take part will be collected electronically by a trained researcher at this initial assessment, the voluntary nature of the research will be highlighted including the right to withdraw at any time.

##### *7.1.6.2 Initial assessment*

All inclusion criteria will be reviewed and a diagnosis of alcohol dependence according to ICD-10 criteria will be confirmed using the Composite International Diagnostic Interview (CIDI; (78)). The

suitability of service users for prescription of acamprosate will be determined by the treating clinician of the specialist alcohol service including clinical assessment and blood investigations according to NICE guidelines. Exclusion criteria will be assessed through interview with the participant to ensure that the service user is suitable to take part in the trial. Participants will be randomised following consent and initial assessment.

Acamprosate will be initiated by the specialist alcohol service in line with the normal clinical practice for the community alcohol service. Prescriptions will be dispensed monthly so that adherence data can be regularly collected by the research team and to ensure reduced loss of MEMS data. The prescription of acamprosate will be made in line with the normal care pathway, the responsibility for which normally transfers from the specialist alcohol team to the persons GP after three months.

#### 7.1.7 Withdrawal of Participants

It will be made clear to potential participants that the clinical care that they receive will not be affected by their decision whether or not to take part in the research and they are free to withdraw at any time without providing a reason for them doing so. Data collected up to the time of withdrawal will be used as appropriate unless the participant wishes for their data not to be used and will therefore be destroyed. Withdrawn subjects will be replaced as far as possible within the constraints of the duration of recruitment. The decision to continue to prescribe acamprosate throughout the trial will be made by the treating clinician in conjunction with the participant. If the decision not to continue prescribing/taking acamprosate is made at any stage of the trial participants will not be withdrawn from the trial and outcomes will still be collected.

#### 7.1.8 Alcohol abstinence

If participants resume alcohol consumption during the trial period this will not exclude them from any aspect of taking part in the trial.

#### 7.1.9 Randomisation

The proposed trial involves differential allocation of the order of 2:1:1 to maximize the utility of resources with twice as many being allocated to the SS group than the intervention groups. Randomisation will be carried out after consent has been gained and the initial baseline assessment has been conducted. A remote randomisation procedure will be used through an online system developed and maintained by Codeface Ltd to generate the treatment allocation, which will be initiated by a trained researcher. It is not possible for participants and the study team to be blind to treatment allocation. Allocation will employ a stratified random permuted block method with stratification by severity of alcohol dependence (SADQ score of  $\leq 30$  or  $>30$ ), site and the prescription of other relapse prevention medication. These variables are known to be related to clinical outcomes and will be collected at preliminary screening.

#### 7.1.10 Data collection

Table 1 outlines the study outcome measures and timing of their administration during the study. Research and personal data will be collected using electronic data capture, specifically designed for this research study by Codeface Ltd, using a laptop computer. Laptop computers will be password protected. Data will be entered and saved on a secure server with a 256bit encryption, no data will be saved directly onto the laptop computer. Research data will be anonymised by assigning

each participant a unique ID number, personal data will be stored separately to the research data to maintain participant anonymity.

All of the study interventions will be audio recorded and a proportion will be reviewed by the research team to check the fidelity of the delivery of the intervention and inform further training. Audio files will be stored on a secure server with restricted access through password protected computers. Consent to take part in the research will be captured using an electronic consent form overseen by the researcher.

Table 1: Trial outcome measures, timing of administration and duration of participant completed questionnaires

		Baseline	Bi-Monthly visit (months 1 to 6)	6 month follow-up	12 month follow-up
CIDI	Diagnosis of alcohol dependence				
ASSIST	Psychoactive drug misuse				
SADQ	Severity of alcohol dependence				
AUQ	Current craving for alcohol				
APQ	Presence of alcohol related problems				
TLFB	Percentage of days abstinent and Units of alcohol per drinking day Time to first alcoholic drink Time to relapse to any drinking Time to relapse to heavy drinking.				
BMQ	Beliefs about medication specific to their health and general medication beliefs				
EQ-5D-5L	Health related quality of life				
AD-SUS	Service use				
STAR	Therapeutic relationship with pharmacist delivering MM				
MMAS	Assess self-reported adherence to acamprosate				
MEMS	Percentage medication taken as prescribed				
Pill count	Percentage of pills taken				
Self-reported adherence	Percentage of pills taken Reasons for non-adherence				

#### *7.1.10.1 Primary outcome measure*

The primary outcome measure will be the percentage of medication taken as prescribed during the 24 weeks target phase of prescribing, post randomisation. The prescription of AC will be two tablets (333mg per tablet) three times a day (morning, afternoon and evening) total daily dose 1998mg) or two tablets in the morning and one tablet in the afternoon and evening (total daily dose of 1665mg) if the service user weighs less than 60kg. Participants will be instructed to take their medication in the morning between 6am and 11am, afternoon between 12pm and 4pm and evening between 5pm and 10pm. If the participant takes the prescribed dose (i.e. two tablets) within the specified time frame, this will be considered adherent. The percentage of medication taken as prescribed will be calculated from the total number of doses taken in relation to the total number of possible doses. Over the 24 week period the maximum number of prescribed doses of acamprosate is 504.

There is no definitive, gold-standard method to determine medication adherence, therefore a triangulated approach will be used with three methods of data collection. The Medication Events Monitoring System (MEMS) has been chosen due to its validity in measuring adherence and it will allow the collection of data relating to the time that the medication was taken (34). MEMS has been used in many clinical trials of adherence to medication for both mental and physical health (34) and alcohol dependence (50, 79-84). In addition pill count and self-report have been chosen as they are the most frequently used in clinical trials and can be implemented into clinical practice (23).

MEMSCap is a trademarked product of MWV Corporation. Microcircuits are integrated into medication bottle caps, which record the time and date when the vial is opened. MEMS software will be purchased to enable the data to be transferred to the trial team's computer system. A participant's MEMSCaps can be reset to allow a new prescription of the trial medication to be dispensed using the same bottle cap, thus minimising costs. All trial participants will be given monthly prescriptions of acamprosate, which will be dispensed on a monthly basis at the designated pharmacy. Participants will be asked to notify the research team if the MEMSCap is lost or broken and it will be replaced as soon as possible. Pill count will also be carried out by the pharmacist to measure adherence to acamprosate. When the participant's prescription is being dispensed, the pharmacists will record the number of pills returned. Participants will be seen bi-monthly by the research team so that the data from the MEMSCaps can be transferred and any issues with the MEMSCaps can also be identified at this stage. Participant self-report will be used to measure adherence by estimating the proportion of medication taken in the previous month. An algorithm has been developed to define the method of combining the three adherence measures into a single measure of adherence based on Swift et al. (22). MEMS is considered a measure which can be interpreted with 'medium' confidence and pill count and self-report are considered to be 'low' confidence measures of adherence. In cases of discrepancy between methods of adherence measurement or if data is missing, the data recorded by MEMS will be taken first, followed by pill count if MEMS is not available, and self-report if both MEMS and pill count data are not available. As part of our analysis we will investigate the concordance between these three measures. If all methods of adherence measurement are missing, participants will be considered to be non-adherent for the reporting period (previous one month).

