#### *7.1.1.1 Treatment arm 1: Standard support (SS)*

All participants in the trial will be prescribed acamprosate (two 333mg tablets morning, afternoon and evening or two 333mg tablets in the morning and one 333mg tablet in the afternoon and evening if the service users body weight is below 60kg) as soon as possible following alcohol abstinence in addition to the psychosocial care normally provided. The decision to initiate acamprosate will be determined by the treating clinician in the specialist alcohol service in conjunction with the service user.

The NICE guideline on diagnosis, assessment and management of harmful drinking and alcohol dependence (13) recommends, "Service users taking acamprosate should stay under supervision, at least monthly, for 6 months, and at reduced but regular intervals if the drug is continued after 6 months" p426. In clinical practice, after completion of assisted alcohol withdrawal, service users remain under the care of the specialist alcohol service for up to three months before they are transferred back to the care of their GP for ongoing care including prescribing. The type, frequency and intensity of psychosocial intervention received vary between specialist alcohol services and between individual service users, dependent on their needs, local funding and services available. As this is a pragmatic RCT, SS will be the care normally provided by local participating services, and service use will be recorded for each participant. However, participating services have agreed to follow the NICE guideline with respect to acamprosate prescribing with trial participants. Based on the current service provision of the five proposed study centres, SS is monthly pick up of prescribed acamprosate from the community pharmacy and monthly monitoring of the service user for three months by the specialist alcohol service and then returned to the care of their GP for monthly monitoring in accordance with the NICE guidelines (13) and current NHS clinical practice. As the trial is pragmatic it will be possible for patients to continue being prescribed acamprosate beyond the 24 week period of medication adherence monitoring providing this is agreed between patients and clinicians, in accordance with NICE guidelines.

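### The daily dose stated for participants under 60 kg is one tablet too high (1665 mg instead of 1332 mg), and the two-tablet definition of an adherent dose does not fit their one-tablet doses

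*Protocol*

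**What the plan says.** Protocol 7.1.10.1 defines the primary outcome as the percentage of medication taken as prescribed over 24 weeks, calculated as doses taken over possible doses. It gives two regimens of 333 mg tablets. The standard one is two tablets three times a day, with a total of 1998 mg. The regimen for participants under 60 kg is "two tablets in the morning and one tablet in the afternoon and evening (total daily dose of 1665mg".

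Protocol 7.1.1.1 gives the same low-weight schedule without a daily total: "two 333mg tablets in the morning and one 333mg tablet in the afternoon and evening if the service users body weight is below 60kg".

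The rule for an adherent dose follows in 7.1.10.1: "If the participant takes the prescribed dose (i.e. two tablets) within the specified time frame, this will be considered adherent". It makes no exception by weight. The denominator is then fixed: "Over the 24 week period the maximum number of prescribed doses of acamprosate is 504".

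The section also describes the three measures:

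- The MEMS caps contain circuits "which record the time and date when the vial is opened".
- For pill count, "the pharmacists will record the number of pills returned".
- For self-report, "Participant self-report will be used to measure adherence by estimating the proportion of medication taken in the previous month".

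Where the measures disagree or data are missing, "the data recorded by MEMS will be taken first, followed by pill count if MEMS is not available", and self-report comes last. Agreement between the three measures is also to be examined.

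**The concern.** Two statements in the definition of the primary outcome conflict with the regimen given beside them. The milligram total for the low-weight group does not follow from its tablet schedule, and the explanation of an adherent dose as two tablets describes only the standard regimen. An analysis plan or scoring program that copies this section would inherit both slips. The measure exposed is pill count, because a percentage of tablets taken needs an expected number of tablets. If that number were taken from the wrong total, or from two tablets at every dose, a fully adherent participant under 60 kg would appear to have missed medication.

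**Working it through.** **Inputs.** Tablet strength is 333 mg (7.1.10.1). The standard schedule is 2+2+2 tablets (7.1.10.1). The low-weight schedule is 2+1+1 (7.1.1.1 and 7.1.10.1). The period is 24 weeks, with three doses a day (7.1.10.1).

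**Figures that reproduce**

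- Standard daily dose: 6 × 333 = 1998 mg, as stated.
- Possible doses: 24 × 7 × 3 = 168 × 3 = 504, as stated. The count is the same for both regimens because each has three doses a day.

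**Figure that does not reproduce**

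- Low-weight daily dose: (2 + 1 + 1) × 333 = 4 × 333 = 1332 mg, against a stated 1665 mg.
- 1665 / 333 = 5 tablets exactly. This would fit a day such as 2+2+1, which appears nowhere in the protocol.
- Excess: 1665 − 1332 = 333 mg, one tablet; 1665 / 1332 = 1.25, so 25% too high.

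Because 1998 mg and 504 both reproduce, rounding or a different tablet strength does not explain the mismatch.

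**The two-tablet rule.** Under 60 kg, the afternoon and evening doses are one tablet each. Over 168 days that is 168 × 2 = 336 of 504 doses (66.7%) that the bracketed explanation misdescribes. This measures the wording and does not predict a score, since none of the three measures records tablets per dose.

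**What could reach the data.** MEMS takes precedence and counts openings, so neither slip alters a MEMS score. Self-report is a proportion from the start. That leaves pill count. Assume a 28-day supply (the protocol says only that dispensing is monthly) and a participant under 60 kg who takes every prescribed tablet, 28 × 4 = 112:

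| Expected tablets taken from | Expected in 28 days | Pill-count adherence |
|---|---|---|
| 2+1+1 schedule | 28 × 4 = 112 | 112/112 = 100% |
| Stated 1665 mg | 28 × 5 = 140 | 112/140 = 80% |
| Two tablets at every dose | 28 × 6 = 168 | 112/168 = 66.7% |

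The last two rows are conditional bounds. The protocol does not say that pill count is scored either way, and it gives neither the share of participants under 60 kg nor the share whose adherence would rest on pill count.

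**The case against.** The best reply is that this is an editorial matter. The outcome is a count of doses over 504, which is right for both regimens, and no milligram quantity enters the outcome, the sample size or the analysis. Prescribing follows the normal care pathway (7.1.6.2), and the treatment description in 7.1.1.1 carries no wrong total, so the figure does not determine what anyone is given. In the adherence rule the governing idea is the prescribed dose, which the same paragraph sets out correctly for both weight groups; the bracket is loose drafting, and read literally it would make full adherence impossible on a regimen just prescribed. Table 1 lists pill count as a percentage of pills taken, and the natural denominator is the number dispensed or prescribed, so the 80% and 66.7% figures describe a scoring method that nobody has proposed. Body weight (under 60 kg or not) is also a covariate in the primary analysis (7.2.4), and any scoring slip would apply by the same rule in every arm.

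All of this bears on weight, and it stands to that extent: it is why the point is minor and why the pill-count figures are only conditional. It does not remove the error. The schedule and the total cannot both be right, and the bracketed words define the dose instead of offering an example. A primary outcome definition should not depend on the reader discarding part of it. Nor is this a detail left to the analysis plan, because the protocol states it and states it wrongly.

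**Conclusion.** The point holds and is minor. The daily total for participants under 60 kg is wrong for the stated schedule: 1332 mg, not 1665 mg. That the total is the faulty element, and not the schedule, is an inference from the schedule appearing twice; either way the two contradict each other. The two-tablet explanation is wrong for two of this group's three daily doses.

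MEMS and self-report scores do not change. Any effect is confined to pill count in participants under 60 kg, whether used as a fallback or compared with MEMS, and arises only if pill count were scored from one of the two faulty statements. No effect on the treatment comparison or on power is shown, and none can be calculated without the share under 60 kg and the share relying on pill count.

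**What to change.** Make two changes in 7.1.10.1:

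1. Ask the clinical lead to confirm the 2+1+1 schedule, then replace 1665 mg with 1332 mg. If five tablets a day were in fact intended, correct the schedule instead, in both 7.1.1.1 and 7.1.10.1.
2. In the adherence rule, replace the bracketed two-tablet explanation with: the number of tablets prescribed for that dose for that participant.

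The 504-dose denominator stays. The cost is one confirmation and two phrases, with no change to design, data collection or sample size.

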#### 7.1.1 Design and theoretical/conceptual framework

The study will be a 3-arm, pragmatic, randomised controlled, parallel group clinical trial. Each participant will be prescribed acamprosate as soon as possible after alcohol abstinence is achieved for a minimum duration of 24 weeks. Follow-up contacts with the research team will take place 6 (+30 days) and 12 (+60 days) months post randomisation. Participants will collect their medication monthly from the community pharmacy, which will be dispensed from designated pharmacies in bottles with MEMSCaps. Consented participants will be randomised (in the order of 2:1:1) to receive;

- SS consisting of monthly pick up of prescribed acamprosate from the community pharmacy and monthly follow-up with their specialist alcohol team for three months followed by monthly follow up with their GP for three months; or
- SS+ MM once a week for the first 6 weeks, reducing to once a fortnight for the following 6 weeks, and then monthly for 3 months, delivered by telephone by a trained pharmacist from a central telephone support service; or
- SS+MM+CM which will include incentivisation for completion of each of the telephone MM support sessions, with the pharmacist.

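### The one-month self-report recall does not match the undefined bi-monthly visits or the 24-week primary window, so an attender lacking both MEMS and pill count can be scored non-adherent by design

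*Protocol*

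**What the plan says.** Section 7.1.10.1 of the protocol defines the outcome: "The primary outcome measure will be the percentage of medication taken as prescribed during the 24 weeks target phase of prescribing, post randomisation". It also gives the denominator: "Over the 24 week period the maximum number of prescribed doses of acamprosate is 504".

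The same section ranks the sources. MEMS is used first, then pill count if MEMS is unavailable, then self-report if neither is available. The caps log openings continuously and are downloaded at research visits: "Participants will be seen bi-monthly by the research team so that the data from the MEMSCaps can be transferred". The pharmacist counts returned pills at each monthly dispensing. For self-report the rule is: "Participant self-report will be used to measure adherence by estimating the proportion of medication taken in the previous month". If all three sources are missing, "participants will be considered to be non-adherent for the reporting period (previous one month").

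Table 1 (section 7.1.10) ticks self-reported adherence under "Bi-Monthly visit (months 1 to 6") and at the 6-month and 12-month follow-ups. Section 7.1.1 sets the timing of those follow-ups: "Follow-up contacts with the research team will take place 6 (+30 days) and 12 (+60 days) months post randomisation". Section 7.2.4 plans multiple imputation and sensitivity analysis for missing data, without saying how these relate to the non-adherent rule.

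**The concern.** A fallback source should be able to supply a value for every period in which it may be needed. Here three things are fixed separately: how far back the question reaches, how often it is asked, and which days count towards the endpoint. They fit together only on one reading of bi-monthly.

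If visits are two months apart, every other month is never asked about. The final question also looks back from the visit date, not from day 168, so a late visit asks about days after the endpoint has closed.

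The first two sources can fail together. The cap sits on the bottle that holds the pills, and the count needs pills to be brought back, so a lost bottle can remove both. Self-report is the only source that needs no returned object. Where it was never asked for, the month is scored as non-adherent although the participant attended and could have answered. That can only lower measured adherence. A later analysis plan cannot recover answers that were never collected.

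**Working it through.** **Inputs from the protocol.** A 24-week window (7.1.10.1), recall of one month (7.1.10.1), bi-monthly visits in months 1 to 6 (Table 1), a 6-month visit with +30 days (7.1.1), and monthly dispensing and pill count (7.1.10.1).

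**Assumptions.** A month is 28, 30 or 30.44 days, with the look-back rounded to whole days. Two-monthly visits fall at months 2, 4 and 6.

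**The plan's own figure.** 24 × 7 = 168 days; 168 × 3 dosing occasions = 504. This reproduces the stated maximum.

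**Reading 1: every two months.** Days with self-report are those in 1-168 that lie within one month before a visit. Days without = 168 − days with. Doses without = 3 × days without.

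| Month (days) | 6-month visit | Days with self-report | Days without | Doses without | Share of window |
|---|---|---|---|---|---|
| 28 | day 168, on time | 28 + 28 + 28 = 84 | 84 | 252 | 50.0% |
| 30 | day 180, on time | 30 + 30 + 18 = 78 | 90 | 270 | 53.6% |
| 30.44 | day 183, on time | 30 + 30 + 15 = 75 | 93 | 279 | 55.4% |
| 28 | day 198, 30 days late | 28 + 28 + 0 = 56 | 112 | 336 | 66.7% |
| 30 | day 210, 30 days late | 30 + 30 + 0 = 60 | 108 | 324 | 64.3% |
| 30.44 | day 213, 30 days late | 30 + 30 + 0 = 60 | 108 | 324 | 64.3% |

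**Reading 2: twice a month.** With the 6-month visit on time, no day lacks self-report. With it 30 days late, 14, 3 or 1 days lack it for months of 28, 30 or 30.44 days (8.3%, 1.8%, 0.6%).

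**The last look-back.** Take 6 months as about day 182 (26 × 7) and a month as 30 days. The look-back from day 182 is days 153-182, and its overlap with the window is days 153-168, or 16 days. From day 198 the look-back starts at day 169 and the overlap is zero. Day 198 is 16 days into the 30 allowed. With 28-day months the nominal visit is day 168 and the whole look-back lies inside the window.

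**From gap to forced zeros.** A day without self-report is not yet a zero. The rule applies only if MEMS and pill count are also missing. Let p be the share of attenders' participant-months lacking both, spread evenly over the window. On reading 1 the share of months with a forced zero is p × 0.50 to p × 0.67. The protocol gives no p. Purely as an illustration, p from 5% to 20% gives 0.05 × 0.50 = 2.5% up to 0.20 × 0.67 = about 13%. The bias in the mean also depends on true adherence in those months, which is unknown.

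**The case against.** The strongest reply is that self-report is only the third tier. A reader might infer from the recall gap that whole months have no fallback and are scored non-adherent, or that a lost cap or unreturned pills alone leads to a zero. The protocol does not support this. The pharmacist's count is tied to monthly dispensing, so it can cover the months that self-report misses. A lost cap leaves the pill count, and unreturned pills leave MEMS. Both must fail in the same month, and section 7.1.10.1 also provides for replacing lost or broken caps.

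Second, the gap hangs on an undefined word. Read as twice a month, it almost disappears. The look-backs then overlap, but overlap in a last-tier source forces no zeros.

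Third, the protocol uses 24 weeks and 6 months almost interchangeably for the primary endpoint. On a 4-week month, an on-time visit misses nothing. Even at day 182, 16 of 30 look-back days lie inside the window, so it would be wrong to say that an on-time visit mostly measures days outside it.

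Fourth, a reader might infer bias between arms. Caps, dispensing, counts and visits are specified alike for all three arms, and nothing in the protocol shows that loss would differ.

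Finally, the protocol mentions an algorithm for combining the measures, and section 7.2.4 plans multiple imputation. Details may sit elsewhere.

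The first four replies stand as limits on the claim. The last does not remove it. The recall period and the zero rule are written in this protocol, and a month scored as zero is not obviously missing for the purpose of imputation.

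**Conclusion.** The mismatch is real but conditional. If bi-monthly means every two months, with visits at months 2, 4 and 6, the third-ranked source cannot exist for 50-55% of the 168 days, or 64-67% if the 6-month visit is 30 days late. In those periods an attender with neither MEMS nor pill count is scored non-adherent by design. If 6 months is about day 182, the last look-back covers at most about 16 days of the window, and none from about day 198. If bi-monthly means twice a month, the gap is nil with an on-time 6-month visit and at most about 8% with one 30 days late.

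The direction is downward for measured adherence. The size is unknown because the protocol gives no rate of joint MEMS and pill-count loss, and a difference between arms cannot be claimed. This is a worthwhile, low-cost improvement. It does not show that the primary outcome is invalid.

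**What to change.** 1. Replace bi-monthly with the actual visit weeks, in section 7.1.10.1 and in Table 1.
2. Keep the visits and change the question. At each research visit, ask for the proportion taken separately for each dispensing month since the last contact. With visits at months 2, 4 and 6, this covers all 168 days.
3. At the 6-month visit, anchor the question to calendar dates ending at day 168 after randomisation, whatever the visit date.
4. Define the reporting period in the non-adherent rule to match these intervals.
5. State in section 7.2.4 whether a month with all three sources missing is scored non-adherent or multiply imputed in the primary analysis, and which of the two is the sensitivity analysis.

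The cost is a reworded question, extra fields in the electronic data capture and a short amendment, with no added visits. The downside is recall of up to about two months. It is somewhat longer at a late 6-month visit: with 30-day months, a visit at day 210 after contact at day 120 reaches back 90 days. That loss of precision falls only on the source already ranked lowest, and only where the other two are missing.
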